8.2. Baseline Characteristics and Poolability of Data

Summaries of subject disposition, demographics, baseline characteristics, and subject accountability will be provided.

Data from all geographies will be pooled for analysis. The poolability is assumed given that study data are collected and managed by a central database under one data management plan, including the use of Data Monitoring Committee (DMC), Clinical Event Committee (CEC), Independent Physician Reviewer (IPR) and core imaging laboratory.

8.3. Handling of Missing Data

During statistical analysis, imputation of missing data will not be performed except for data related to the onset date of an adverse event or a death. In cases where the onset date of an event or a death is incomplete and unresolvable via data query, the 15th day of the known month or July 1st of the known year will be used.

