Screening CT/MRA images will be sent to a core lab to assess the anatomical inclusion/exclusion requirements. An Independent Physician Reviewer (IPR) will review screening CT/MRA images to determine eligibility. Approval by the IPR must be obtained prior to a subject's enrollment in the study. The decision of the IPR will be communicated to the investigational site by the Sponsor. Those subjects who sign and date the Informed Consent, meet all study eligibility criteria, and are approved by the IPR will be eligible for enrollment. Subjects that are not approved by the IPR are considered screen failures and will not be enrolled in the study.

Subjects who do not qualify for enrollment will be documented as ineligible on the Screening and Enrollment log.

Enrollment:

Those subjects who sign and date the informed consent document, meet all of the study eligibility criteria, and are approved by the IPR will be eligible for enrollment into the Endurant Evo International Clinical Trial. The subject will be considered to be enrolled when arterial access has been established with an attempt to introduce the Endurant Evo AAA stent graft.

Enrolled subjects will be documented on the Screening and Enrollment Log. Subjects who are enrolled, but not implanted with the device will be followed through the 1 month follow-up only.

The investigator will maintain a log of all subjects screened and enrolled in the clinical study, assigning an identification code linked to their names, alternative subject identification or contact information.

F.2 Implant and Follow up

F.2.1 Index Procedure

All investigators will read, understand and be trained to the Endurant Evo AAA stent graft system Instructions for Use (IFU) prior to initiation of the procedure. The IFU is packaged with the device and must be followed for implantation of the stent graft system.

Identification and/or serial numbers for all investigational components of the Endurant Evo AAA stent graft system used or opened during the index procedure will be recorded.

Adverse event assessment should be done for all subjects as of the moment the subject is considered to be enrolled in the study.

F.2.1.2 Treatment failure

Inability to implant the Endurant Evo AAA stent graft system following arterial access due to deployment issues or entrapment of the delivery system will be considered a treatment failure. These subjects will be followed through the 1-month follow-up time point and then exited from the study.

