8.1. General consideration

All endpoints will be analyzed descriptively. In general, qualitative parameters will be described by their distribution frequencies; quantitative parameters will be described by their mean, standard deviation, minimum, maximum, median, and number of subjects with assessable data.

The survival from all-cause mortality over one year time or longer will be described by the Kaplan-Meier survival curve and the associated Kaplan-Meier estimate will be calculated along with its standard error using the Greenwood method.

For events such as AEs, deaths and secondary procedures, that can occur or are observed at any time during the study, no time window will be applied. For such events, an event that occurs “within 1 month or 30 days” is an event that takes place between Days 0 to 30, inclusive.

Similarly, an event that occurs “within 12 months or 365 days” is an event occurring between Day 0 to Day 365, inclusive. Date of event onset will be used to determine when the event occurred. Day 0 is referring to the day of index procedure.

For image-based assessments, such as stent-graft endoleak, patency, and other observations, the following time windows will be applied for by-visit data summaries:

Table 1: Time Windows for Statistical Analyses

Study Visit	Target Day	Time Window
Implant	Day 0	Day 0
1 Month	Day 30	1 – 90 days
6 Months	Day 183	91 – 304 days
12 Months	Day 365	305 – 548 days
2 Year	Day 731	549 – 913 days
3 Year	Day 1096	914 – 1278 days
4 Year	Day 1461	1279 – 1644 days
5 Year	Day 1826	1645 – 2009 days

If different type of images are used but have different finding in the same time window, the imaging technique and sensitivity matrix (Appendix 12.1) will be applied. Finding from higher visibility image will be used for analysis. If there are two or more assessments from the same type of image in the same time window, then the assessment closest to the target day will be used in the analysis of event rate at a given time point.

Statistical analyses for this study will be performed using the Statistical Analysis System (SAS) for Windows (Version 9.1 or higher) or other widely-accepted statistical or graphical software.

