8.4. Analysis of the Primary Endpoints

For the primary endpoint, a one-sided 95% confidence interval based on binomial distribution will be constructed in addition to event count and frequency.

The analysis for the regulatory submission will take place when 40 subjects have been implanted with the study device for at least 30 days except that a subject expires early. Endpoints as defined in Section 5 will be analyzed for these 40 ITT subjects.

MAE Rate Calculation:

All MAEs will be adjudicated by the Clinical Event Committee (CEC) per protocol except for the procedural blood loss ≥ 1000 cc, which will be site reported at the index procedure. MAE rate will be calculated as follows (Table 2):

Table 2: MAE Rate Calculation:

MAE rate = $m/(m + k)$	Within 30 Days	Within 183 Days	Within 365 Days
$m = \text{No. of Subjects Who Had MAE(s)}$	No. of subjects who had at least one MAE with onset day from Day 0 to Day 30, inclusive.	No. of subjects who had at least one MAE with onset day from Day 31 to Day 183, inclusive.	No. of subjects who had at least one MAE with onset day from Day 184 to Day 365, inclusive.
$k = \text{No. of Subjects Who Had No MAE}$	No. of subjects who have been in study for at least 1 day and without an MAE.	No. of subjects who have been in study for at least 91 days and without an MAE.	No. of subjects who have been in study for at least 305 days and without an MAE.

If a subject is early terminated from the study, the last day that the subject has been seen will be the duration in study, which can be the day of last follow-up, last imaging taken, an AE reported, or withdrawal from the study. If a subject is still in the study, the duration in study will be the time from index procedure to the cut off day that the database is locked or data snapshot is taken.

Imaging based Event Rate Calculation:

Imaging assessment will be performed by site as well as the core lab. Assessments from the core lab will be analyzed separately from those by site. Imaging based event rate will be calculated using statistical analysis windows as follows (Table 3):

Table 3: Imaging based Event Rate Calculation:

Event rate = m/n	At 1 Month	At 6 Months	At 12 Months
$m = \text{No. of Subjects Who Had Event(s)}$	No. of subjects who had an event with scan day within the 1-month window.	No. of subjects who had an event with scan day within the 6-month window.	No. of subjects who had an event with scan day within the 12-month window.

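### The partial-date rule has no bound at the index procedure, death or last contact, so a post-procedure MAE or death with an unresolved date can be given an impossible date

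*SAP*

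**What the plan says.** SAP 8.3 allows no imputation except for event onset and death dates. The exception applies only to partial dates that queries have failed to complete; for those, "the 15th day of the known month or July 1st of the known year will be used". Protocol H.1 gives the same rule. Neither text relates the imputed date to the index procedure, to death or to last contact.

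The date matters because SAP 8.1 places events in time by it: "Date of event onset will be used to determine when the event occurred". The same section says "Day 0 is referring to the day of index procedure", and that an event within 30 days "is an event that takes place between Days 0 to 30, inclusive". In SAP 8.4, Table 2, the 30-day numerator m is "No. of subjects who had at least one MAE with onset day from Day 0 to Day 30, inclusive", and the non-event count k is "No. of subjects who have been in study for at least 1 day and without an MAE". The other two columns of Table 2 take onsets on Days 31-183 and Days 184-365.

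Protocol F.2.1 fixes when event collection starts: "Adverse event assessment should be done for all subjects as of the moment the subject is considered to be enrolled in the study". Under protocol F.1, enrollment occurs at arterial access with an attempt to introduce the device.

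**The concern.** Event collection starts at the index procedure, so a recorded event should not have a true onset before Day 0. The imputation rule can still give it one, because the substituted date depends only on the calendar. The result is an impossible date, which is different from the ordinary error of mid-period imputation.

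An MAE with a negative study day misses all three columns of Table 2, so no numerator counts it. Table 2 also does not say whether that subject still counts as being without an MAE in k. For a death, the Kaplan-Meier time could be negative. In the other direction, an onset could be dated after the subject's death or last contact.

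The planning assumption in SAP 3.2 is two MAEs in 40 subjects, so a single misdated event would visibly change the primary safety rate.

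**Working it through.** **Inputs from the documents.** Imputation rule (SAP 8.3, protocol H.1); Day 0 and onset-date convention (SAP 8.1); m and k (SAP 8.4, Table 2); 2 of 40 expected MAEs and a margin of error below 10% (SAP 3.2); one-sided 95% binomial interval (SAP 8.4).

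**Assumptions.** Index dates are uniform over a 365-day year and onset days are uniform within each range shown. The documents give neither distribution. All percentages are conditional on a date that is still incomplete after query.

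**1. The plan's own figure.** The exact one-sided 95% upper limit for x events in n is the 95th percentile of Beta(x+1, n−x). For 2/40, Beta(3, 38) gives 14.92%. The margin is 14.92 − 5.00 = 9.92 points, which agrees with the stated figure of below 10%.

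**2. Worked example (assumed dates).** Index procedure on 20 September, MAE in September with the day unknown: imputed to 15 September, Day −5. If only the year is known: imputed to 1 July, Day −81. Neither date falls in any column of Table 2.

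**3. Only the day missing.** Imputed study day = 15th of the onset month − index date, over every index date and onset day.

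| True onset | Dated before Day 0 | Dated after Day 30 |
|---|---|---|
| Day 0-3 | 668/1,460 = 45.8% | 0 |
| Day 0-5 | 930/2,190 = 42.5% | 0 |
| Day 0-7 | 1,144/2,920 = 39.2% | 0 |
| Day 0-30 | 1,523/11,315 = 13.5% | 1,260/11,315 = 11.1% |

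A date before Day 0 arises when the index day is after the 15th (185/365 = 50.7% of dates) and onset is in the same month. The error is at most 16 days (15 − 31). An early onset can only be lost backwards: to be dated after Day 30 it must fall in the month after an index procedure done in about the first half of the previous month, and no onset before Day 17 met that condition.

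**4. Only the year known.** Of true Day 0-30 onsets, 46.0% are dated before Day 0 and 45.5% after Day 30, so 91.5% fall outside the window.

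**5. Movement the other way.** With only the day missing, 13.5% of true Day 31-61 onsets, and 27.7% of Day 31-45 onsets, are imputed into Day 0-30.

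**6. Effect of losing one of two MAEs.**

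| Reading of Table 2 | Rate | Exact one-sided 95% upper limit |
|---|---|---|
| Both counted | 2/40 = 5.0% | 14.9% |
| One lost, subject counted in k | 1/40 = 2.5% | 11.3% |
| One lost, subject in neither m nor k | 1/39 = 2.6% | 11.6% |

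**7. After a floor at the index date.** No event is dated before Day 0. With the day missing, the share of true Day 0-30 onsets kept in the window rises from 75.4% to 75.4 + 13.5 = 88.9%. With only the year known it rises from 8.5% to 8.5 + 46.0 = 54.5%. The onsets dated after Day 30 are unaffected.

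**The case against.** The strongest reply is that the rule may never be applied to a 30-day MAE. It applies only after queries have failed, and early events are the best documented:

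- Events are assessed at the procedure, at discharge and at 1 month (protocol Table F-2).
- Serious events reach the sponsor within 3 calendar days (Table F-4).
- All eCRF data need source documents (G.1.2).
- The CEC adjudicates every MAE except procedural blood loss (F.6.5), and blood loss is dated by the procedure itself (L.2).
- Consistency checks (SAP 10) could also reveal a negative study day.

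This stands as a limit on size. A year-only date for a 30-day event is hard to imagine, so 91.5% shows how the rule behaves rather than what to expect. It does not repair the rule: no text tells the analyst or the CEC to reset an impossible date, and protocol section H requires departures from the analysis section to be described and justified in the final report.

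A second reply is that the trial is descriptive, with no hypothesis or success threshold (protocol C.3, SAP 3.3), so no formal decision depends on one event. That also stands. It limits what is at stake, but the reported rate would still be wrong.

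Two stronger readings are tempting, and the documents do not support either. A reader might infer that the rule generally understates risk. That is firm only for early onsets with the day missing. Step 5 shows gains as well as losses, and the balance depends on how MAEs are spread over time, which the documents do not quantify. A reader might also count the 11.1% dated after Day 30 as the same defect. Those dates are possible ones, and their error is the usual cost of imputing a mid-month day.

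**Conclusion.** The point holds in a limited form. Followed as written, the rule can give a post-procedure MAE or death an impossible date, and an MAE dated before Day 0 is counted in no column of Table 2. This is a stated rule that gives a wrong result, rather than a missing detail.

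Given an unresolved day and uniform dates, the share dated before Day 0 is about 46% for Day 0-3 onsets and 13.5% for Day 0-30 onsets. How often a date stays unresolved is not stated and is probably low for 30-day events. If it affects one of two expected MAEs and that subject has no other validly dated 30-day MAE, the reported rate falls from 5.0% to 2.5% or 2.6%. The net direction over all events is not established. The correction should be made because it is cheap and the rule is wrong, not because a large bias has been shown.

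**What to change.** Add to SAP 8.3 and protocol H.1: *If the imputed date precedes the index procedure and the known part of the date is compatible with onset on or after it, use the index date; if it follows death or last known contact, use that date.*

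As a sensitivity analysis only, count any MAE whose partial date is compatible with Day 0-30 as within 30 days. This should not be the primary rule. It would make worst-case classification the default, and an event imputed to Day 40 could then be counted in the 30-day column by compatibility and in the Day 31-183 column by date.

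The cost is a few sentences and a short programming change, with no new data: the index date is recorded, protocol F.7.3 provides for the date last known alive, and SAP 8.4 already uses the last day seen. The stated rate may become slightly less favourable. Enrollment has closed at 69 subjects, so the sponsor can check whether any 30-day event has a partial date and report the number.

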8.4. Analysis of the Primary Endpoints

For the primary endpoint, a one-sided 95% confidence interval based on binomial distribution will be constructed in addition to event count and frequency.

The analysis for the regulatory submission will take place when 40 subjects have been implanted with the study device for at least 30 days except that a subject expires early. Endpoints as defined in Section 5 will be analyzed for these 40 ITT subjects.

MAE Rate Calculation:

All MAEs will be adjudicated by the Clinical Event Committee (CEC) per protocol except for the procedural blood loss ≥ 1000 cc, which will be site reported at the index procedure. MAE rate will be calculated as follows (Table 2):

Table 2: MAE Rate Calculation:

MAE rate = $m/(m + k)$	Within 30 Days	Within 183 Days	Within 365 Days
$m = \text{No. of Subjects Who Had MAE(s)}$	No. of subjects who had at least one MAE with onset day from Day 0 to Day 30, inclusive.	No. of subjects who had at least one MAE with onset day from Day 31 to Day 183, inclusive.	No. of subjects who had at least one MAE with onset day from Day 184 to Day 365, inclusive.
$k = \text{No. of Subjects Who Had No MAE}$	No. of subjects who have been in study for at least 1 day and without an MAE.	No. of subjects who have been in study for at least 91 days and without an MAE.	No. of subjects who have been in study for at least 305 days and without an MAE.

If a subject is early terminated from the study, the last day that the subject has been seen will be the duration in study, which can be the day of last follow-up, last imaging taken, an AE reported, or withdrawal from the study. If a subject is still in the study, the duration in study will be the time from index procedure to the cut off day that the database is locked or data snapshot is taken.

Imaging based Event Rate Calculation:

Imaging assessment will be performed by site as well as the core lab. Assessments from the core lab will be analyzed separately from those by site. Imaging based event rate will be calculated using statistical analysis windows as follows (Table 3):

Table 3: Imaging based Event Rate Calculation:

Event rate = m/n	At 1 Month	At 6 Months	At 12 Months
$m = \text{No. of Subjects Who Had Event(s)}$	No. of subjects who had an event with scan day within the 1-month window.	No. of subjects who had an event with scan day within the 6-month window.	No. of subjects who had an event with scan day within the 12-month window.
$n = \text{No. of Subjects Who Had Readable Images}$	No. of subjects who had a readable image within the 1-month window.	No. of subjects who had a readable image within the 6-month window.	No. of subjects who had a readable image within the 12-month window.
Event rate = m/n	Through 1 Month	Through 6 Months	Through 12 Months
$m = \text{No. of Subjects Who Had Event(s)}$	No. of subjects who had an event with scan day within the 1-month window.	No. of subjects who had an event with scan day within 1- or 6-month windows.	No. of subjects who had an event with scan day within 1-, 6- or 12-month windows.
$n = \text{No. of Subjects Who Had Readable Images}$	No. of subjects who had a readable image within the 1-month window.	No. of subjects who had an event (counted in m) or had a readable image	No. of subjects who had an event (counted in m) or had a readable image

		within the 6-month window.	within the 12-month window.
--	--	----------------------------	-----------------------------

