The study population will include those subjects who are appropriate candidates for endovascular repair of infrarenal abdominal aortic or aortoiliac aneurysms, and who meet the Inclusion/Exclusion criteria (defined in Section D).

C.5 Study design

The Endurant Evo International Clinical Trial is a prospective multi-center, pre-market, non-randomized, single-arm trial. The trial is designed to assess the clinical safety and performance of the Endurant Evo AAA stent graft system. A sample of 40 subjects will be enrolled consecutively and evaluated at the 30-day primary safety endpoint. Data from these 40 subjects will be analyzed and used to support regulatory approval. All subjects enrolled will continue to be followed under this investigational protocol beyond the 30-day primary endpoint until 5 years post-implantation.

Given the DDs with SAE potential that have occurred within the Endurant Evo trials (transition stent fracture, partial suprarenal stent detachment, and suprarenal stent fracture), enrollment was terminated with a total enrollment of 69 subjects.

Subjects will have required follow-up evaluations at the following time points:

- 1 month following the index procedure
- 6 months following the index procedure
- 12 months following the index procedure
- Annually thereafter, until 5 years post index procedure

Given the DDs with SAE potential that have occurred within the Endurant Evo trials, the Data Monitoring Committee (DMC) has made additional imaging surveillance recommendations, beyond the required follow-up in the protocol. The additional imaging surveillance recommendations are provided, under separate cover, in the most recent DMC Surveillance and Management letter that has been provided to each investigational site.

In addition to the 40 subjects enrolled to support regulatory approval, approximately 30 additional subjects may be enrolled to support geography-specific regulatory requirements. For these subjects, all inclusion/exclusion criteria, study methods, follow-up schedule and data-collected will be identical to the first 40 subjects enrolled.

Number of devices being used within this trial

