For subjects that are treated with the bifurcated stent graft minimal 3 pieces will be implanted in the target segment; one bifurcated stent graft component and 2 limb stent graft components. For subjects that are treated with the AUI component approximately 2 pieces will be implanted in the target segment; the AUI stent graft component and one limb stent component. Additional stent graft extensions might be needed to cover the complete target lesion length.

C.6 Randomization and blinding

The study is a single arm study, therefore neither randomization nor blinding are applicable to this clinical trial.

C.7 Sample size

A sample of 40 subjects will be enrolled consecutively and analyzed to support regulatory approval. The sample size of 40 subjects is considered adequate to assess the primary safety endpoint, which is defined as the proportion of subjects experiencing a MAE within 30 days post-implantation. Considering the reported MAE rate from the ENGAGE Post-Approval Study (PAS), which evaluated the long-term safety and effectiveness of the Endurant Stent graft system in 328 subjects¹⁸, it is estimated that 2 of 40 (5%) subjects treated with Endurant Evo AAA stent graft system will experience a MAE. The precision of this assumed 5% point estimate can be assessed by calculating the difference from the 1-sided 95% upper confidence limit. This difference, or margin of error, is calculated to be < 10% for the Endurant Evo International Clinical Trial and is therefore considered adequate to assess the primary safety endpoint.

C.8 Number of investigational sites and study duration

Approximately 10 sites will participate in the clinical study. For the initial 40 subjects to be analyzed, no more than 20% (i.e. 8 subjects) will be enrolled from a single investigational site. Enrollment will be halted at sites that reach the 20% enrollment cap. Following enrollment of the 40 subjects, a site where enrollment has been halted may resume enrolling until approximately 30 additional subjects have been reached in total. For the total cohort (approximately 70 subjects) again no more than 20% of the subjects will be enrolled from a single investigational site.¹

The total enrollment period is not expected to exceed 12 months. All enrolled subjects will be followed until 5 years post-implantation. Thus total study duration from first subject enrolled to final subject exit could approach 6 years.

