Implant	Day 0	Day 0
1 Month	Day 30	1 – 90 days
6 Months	Day 183	91 – 304 days
12 Months	Day 365	305 – 548 days
2 Year	Day 731	549 – 913 days
3 Year	Day 1096	914 – 1278 days
4 Year	Day 1461	1279 – 1644 days
5 Year	Day 1826	1645 – 2009 days

If there are two or more assessments in the same time window, then the assessment closest to the target day will be used in the analysis of event rate at a given time point.

In addition to endpoints, summaries of subject disposition, demographics, baseline characteristics, and subject accountability will be provided.

During statistical analysis, imputation of missing data will not be performed except for data related to the onset date of an adverse event or a death. In cases where the onset date of an event or a death is incomplete and unresolvable via data query, the 15th day of the known month or July 1st of the known year will be used.

Statistical analyses for this study will be performed using the Statistical Analysis System (SAS) for Windows (Version 9.1 or higher) or other widely-accepted statistical or graphical software.

Analysis for the regulatory submission:

For the primary endpoint, a one-sided 95% confidence interval based on binomial distribution will be constructed in addition to event count and frequency. Subset analysis will be performed by-sex for the primary endpoints descriptively and reviewed for clinical significant difference. All analysis will be performed on the intent-to-treat analysis set, which includes all enrolled subjects. Subjects will be considered as enrolled in the study as described in section F.1.

The analysis for the regulatory submission will take place when 40 subjects have been implanted with the study device for at least 30 days except that a subject expires early.² Endpoints as defined in Section C.2 will be analyzed for these 40 enrolled subjects.

Interim Analysis:

No interim analysis is planned prior to the regulatory submission.

Annual Report:

An annual report will be provided including all enrolled subjects at the time of reporting if required per local law and regulations.

H.2 Publication Policy

Publications and presentations referring to this clinical study will be coordinated by Medtronic to allow the use of all available data. The following publication policy will have to be adhered to by all participating investigational sites:

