4.1. Primary analysis set

All analysis will be performed on the intent-to-treat (ITT) analysis set, which includes all subjects who underwent the arterial access with an attempt to introduce the Endurant Evo AAA stent graft.

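### The 40-subject regulatory analysis is triggered by an implanted count but analysed as ITT; read literally, failed deliveries drop out, which cannot lower technical success and normally raises it

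*SAP*

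**What the plan says.** The regulatory analysis takes place "when 40 subjects have been implanted with the study device for at least 30 days except that a subject expires early" (SAP 8.4; Protocol H.1 has the same trigger). The next sentence names the subjects to be analysed. In the SAP it is "Endpoints as defined in Section 5 will be analyzed for these 40 ITT subjects"; in the protocol it is "Endpoints as defined in Section C.2 will be analyzed for these 40 enrolled subjects".

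The population rule is stated separately. Protocol H.1, just before the trigger: "All analysis will be performed on the intent-to-treat analysis set, which includes all enrolled subjects". SAP 4.1: "All analysis will be performed on the intent-to-treat (ITT) analysis set, which includes all subjects who underwent the arterial access with an attempt" (the attempt being introduction of the graft). H.1 refers to F.1 for the point of enrolment, and F.1 gives the same criterion as SAP 4.1. F.1 also provides for subjects who are enrolled but receive no device and follows them to 1 month. F.2.1.2 classes inability to implant after arterial access as treatment failure.

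The protocol describes the sample by enrolment: "A sample of 40 subjects will be enrolled consecutively and evaluated at the 30-day primary safety endpoint" (C.5) and "A sample of 40 subjects will be enrolled consecutively and analyzed to support regulatory approval" (C.7). C.5 also refers to "data-collected will be identical to the first 40 subjects enrolled". The parallel sample sentences in SAP 3.1 and 3.2 say treated where the protocol says enrolled.

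**The concern.** The words *these 40* point back to the 40 implanted subjects, yet the same sentence calls them ITT or enrolled subjects. The two descriptions fit the same people only if no delivery fails. Neither document says whether a failed delivery takes one of the 40 places, is added to them, or is left out.

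This matters because the implanted count selects on the outcome. The primary effectiveness endpoint requires successful delivery, deployment and removal of the delivery system, so a subject in whom the graft could not be implanted is always a technical failure. A count restricted to implanted subjects removes certain failures from the denominator and fills their places with later subjects who may succeed. These 40 subjects supply the primary rates and one-sided limits intended to support regulatory approval, so their denominator should have one meaning.

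**Working it through.** **Inputs.** From the documents: n = 40; one-sided 95% binomial limits (H.1, SAP 8.4); an assumed MAE count of 2 in 40 with a margin of error below 10% (C.7, SAP 3.2). Not in the documents: any failed-delivery rate. All counts and rates of failed delivery below are assumptions. The plan does not say which side the interval for technical success takes; I use the lower limit.

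**The plan's own figure.** Exact upper limit for x/n = 95th percentile of Beta(x + 1, n − x). For 2/40 this is 14.92%, so the margin is 14.92 − 5.00 = 9.92 points. The stated figure of less than 10% reproduces, and I use exact limits throughout.

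**Direction for technical success.**

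- Against the first 40 enrolled: let g of them be failed deliveries, and let S be the successes among the other 40 − g. The first 40 enrolled give S/40. The first 40 implanted are those 40 − g plus g later implanted subjects, of whom s succeed (0 ≤ s ≤ g), giving (S + s)/40. The difference is s/40, which is never negative and is at most 2.5 points per failed delivery. It is zero only if every added subject is also a technical failure.
- Against all enrolled up to the 40th implantation: with f failed deliveries and u other technical failures, (40 − u)/40 ≥ (40 − u)/(40 + f).

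**Size.** Assume every implanted subject succeeds and no failed delivery occurs among the added subjects. Exact lower limit for x/n = 5th percentile of Beta(x, n − x + 1); for 40/40 this is 0.05^(1/40) = 92.8%.

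| Failed deliveries | First 40 implanted | First 40 enrolled | All enrolled up to 40th implantation |
|---|---|---|---|
| 0 | 40/40 = 100% (92.8%) | 40/40 = 100% (92.8%) | 40/40 = 100% (92.8%) |
| 1 | 40/40 = 100% (92.8%) | 39/40 = 97.5% (88.7%) | 40/41 = 97.6% (88.9%) |
| 2 | 40/40 = 100% (92.8%) | 38/40 = 95.0% (85.1%) | 40/42 = 95.2% (85.8%) |
| 3 | 40/40 = 100% (92.8%) | 37/40 = 92.5% (81.7%) | 40/43 = 93.0% (82.9%) |

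Between the first 40 implanted and the first 40 enrolled, the lower limit differs by 4.1, 7.7 and 11.0 points for one, two and three failed deliveries.

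**Chance that the sets differ.** P(at least one failed delivery in the first 40 enrolled) = 1 − (1 − p)^40: 18%, 33%, 55% and 70% at assumed p of 0.5%, 1%, 2% and 3%.

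**30-day MAE.** Take 2/40 = 5.0% (upper limit 14.9%) in the implanted 40, with two failed deliveries. If both failed deliveries had an MAE and neither added subject did, the first 40 enrolled give 4/40 = 10.0% (21.4%). If neither failed delivery had one and one added subject did, they give 1/40 = 2.5% (11.3%). There is no fixed direction.

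**The case against.** The strongest reply is that the defined terms govern and the trigger only sets timing. H.1 and SAP 4.1 put every analysis on the ITT set, the sentence after the trigger uses the defined terms, and C.5 and C.7 count by consecutive enrolment. The documents also use implant loosely: the Day 0 row of the analysis-window table is labelled Implant although Day 0 is the index procedure, and the safety endpoint runs from implantation although it is analysed on ITT. Read strictly, that endpoint would have no time zero for a non-implanted subject. This stands, and ITT is probably what is intended. It does not make the trigger workable: with f failed deliveries, 40 + f subjects are enrolled by the 40th implantation, and the text does not say which 40 are meant.

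A reader might infer more than the documents support:

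- *That treated in SAP 3.1 and 3.2 is a second contradiction.* SAP 3.1 uses treated and enrolled interchangeably in its site-cap sentences, so this is loose wording.
- *That the report could stay silent on the matter.* Disposition and accountability summaries are planned, Section H requires deviations from it to be described and justified, and the table shells are a separate document not available here. One can say only that the available text does not ask for this statement.
- *That the no-replacement rule in F.7 settles it.* That rule concerns premature discontinuation, and its examples are withdrawal and loss to follow-up.

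It is also fair to say that the trial is descriptive, with no hypothesis or performance threshold, so no pass/fail decision turns on this.

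**Conclusion.** The inconsistency is real and lies in the current text of both documents. Most of the text favours counting failed deliveries, so the documents do not show that such subjects will be or were left out, or that any reported rate is inflated. What they show is that the literal trigger permits it, in a direction that cannot lower technical success and normally raises it. One failed delivery among the first 40 enrolled would move the estimate by up to 2.5 points and, if every implanted subject succeeds, the lower limit by 4.1 points. These sizes are illustrations that rest on assumed failure counts. With no failed delivery all readings agree. The MAE rate can move either way. The correction is worth making because it is cheap and removes a possible favourable bias in a primary endpoint; confidence is medium.

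**What to change.** In Protocol H.1 and SAP 8.4, replace the implanted count with the first 40 consecutively enrolled subjects per F.1, whether or not implanted, analysed once each has reached Day 30 after the index procedure, died or exited. The endpoint definition already makes a failed delivery a technical failure, so no further rule is needed. For consistency, change treated to enrolled in the sample sentences of SAP 3.1 and 3.2; this is tidying.

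If the analysis has already been run, state in the study report how many enrolled subjects were not implanted and whether they were among the 40.

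The cost is wording in two sections and the SAP sample sentences, or one statement in the report. No new subjects or data are needed, and enrolment has already ended at 69. The downside is that technical success may come out slightly less favourable.
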